The Cegedim LPD obtains medical information from proprietary practice management software used during physician office visits to capture clinical data in an electronic medical record system. Physicians use the practice management software developed by Cegedim to maintain electronic medical records of their patients. In each country a panel of physicians using this electronic system volunteered to make available anonymized patient-level information from their practices for clinical research purposes. Since these data are being collected in usual clinical care in a non-interventional way, they reflect routine clinical practice in these countries. The panel of contributing physicians is maintained as a representative sample of the primary care physician population in each country according to age, sex, and geographical distribution. Additionally in most countries (including Spain and Italy), the patient population is representative of the respective country population according to age and sex distribution, as provided by national statistic authorities.

Table 2: Doctor and patient populations in the Cegedim LPD by country

	Italy	Spain
Number of physicians in the panel	700	300
Average number of patients who consulted GP at least once in a year	800,000	320,000

The patient data in the LPD form a nationally representative sample. Data have been collected in Italy since 2004 and in Spain since 2006, providing several years of medical history, including comorbidity and concomitant medication use information. Of the patients included in the Spanish and Italian LPD, there are currently approximately 68,000 women with drug-treated osteoporosis. Between 1 and 6% of these patients are taking raloxifene, depending on the region; most of the rest are prescribed a bisphosphonate (Cegedim, data on file).

Data are entered regularly during usual patient care, submitted daily to the Cegedim coordinating center, cleaned and de-identified, and then made available for research.

Anonymized patient data collected from each GP practice includes:

- *Demographic information (age, gender)*
- *Medical history (event dates, diagnoses, risk factors, referrals to specialists)*
- *Therapeutic history (date/length of prescription, molecule/product, dosage)*
- *Additional information (test results, immunizations, height, weight, blood pressure)*

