5.4 SUBGROUPS

Age stratified randomly selected subgroup

In the current dataset, there are 1,823 patients in the bazedoxifene group and 82,041 patients in the bisphosphonate group. This means that there is more than 40 times the number of subjects in the bisphosphonate group compared to the number of subjects in the bazedoxifene group. To limit the number of patients in the bisphosphonate group, an age stratified random subgroup will be selected. Based on the sample size and relative risk estimates provided in the final study protocol (study protocol section 7.1, Sample size calculation), the 1,823 bazedoxifene subjects will be adequately matched by a ratio of 1:6 bisphosphonate subjects. Therefore $1,823 \times 6 = 10,938$ bisphosphonate treated subjects are needed to be randomly selected from the total of 82,041 bisphosphonate treated subjects.

Selection scheme: The age of subjects in the study will be categorized into 4 groups (45-49, 50-59, 60-69, and ≥ 70). In the bisphosphonate group, the percentage of subjects in each of these age groups is 1.4%, 13.7%, 28.7%, and 56.2% respectively. To maintain the same proportion of subjects in each age group for the bisphosphonate subgroup, there will be $1.4\% \times 10,938 = 153$ bisphosphonate treated subjects randomly selected from the 45-49 age group; $13.7\% \times 10,938 = 1,499$ subjects randomly selected from the 50-59 age group; $28.7\% \times 10,938 = 3,139$ subjects randomly selected from the 60-69 age group; $56.2\% \times 10,938 = 6,147$ subjects randomly selected from ≥ 70 age group.

Incident cases of study endpoints

Women with a history of study end points recorded prior to the index prescription will not be included in the analysis for that specific outcome, but will be analyzed separately as subgroups for each study end point. The analyses of the primary and secondary endpoints will be performed using these incident cases of study endpoints subgroups.

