For example, a woman with a history of VTE period prior to the index prescription will be categorized as a prevalent case and will be excluded from the primary VTE analysis. A separate analysis for subgroup of women with a medical history of VTE will be performed and the woman would remain eligible for the analysis of other outcomes as normal. Depending on the number of patients in these subgroups of prevalent cases of each endpoint, this supplemental analysis is likely to have low power to perform any statistical comparison and will be descriptive in nature.

Incident/new user subgroup

In this subgroup analysis, cohorts of incident and not prevalent users of bisphosphonate and raloxifene will be compared to a cohort of incident BZA users. Patients will be defined as incident/new user if they have not had any treatment for osteoporosis in at least 6 months prior to the index date. The index date for each patient is the date of the first recorded prescription for BZA or bisphosphonate or raloxifene during the study enrolment/accrual period.

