8.1.4 TIME TO EVENT ANALYSIS

A time to event analysis to compare the risk between treatment cohorts, i.e., the BZA, raloxifene and bisphosphonate treated groups, will be conducted for the primary end point (VTE) and other secondary endpoints if sufficient data are available,

[figure not shown]
The time to an event will be calculated as the time from index prescription date to the incidence date of primary end points. If a patient does not have a primary end point, the treatment duration will be based upon the index prescription date to the last visit or end of follow-up period, whichever comes first.

In order to ensure the exact duration from the start of treatment to the incidence of primary endpoints, a subgroup of newly prescribed patients who were diagnosed with osteoporosis during the enrolment period will be used first.

In the very unlikely event that the number of bisphosphonate or raloxifene patients are less than the number of BZA patients, the analysis will be extended to include bisphosphonate and raloxifene patients whose treatment began prior to the enrolment period. Considering the fact that bisphosphonates and raloxifene were launched before BZA (See the figure below), some patients could have already gotten treatment of bisphosphonates and raloxifene prior to the enrolment period (i.e., before BZA was launched). For such patients the start date will be the first date of treatment for bisphosphonates or raloxifene, available within the database.

Figure 1. Calculation of duration (from start date to the incidence of primary endpoint) for the treatment cohorts

The time to event analysis model will also be used to test for differences in time to event while adjusting for covariates of interest.

This model will take into account the duration to the incidence of the endpoint and control for imbalances in outcome risk factors, as determined based on the baseline descriptive analysis.

The following factors possibly related to the incidence of the primary end point will be considered.

- Treatment group (BZA, raloxifene, and bisphosphonate)
- Age
- BMI
- Reported history of smoking (If the reported frequency of smoking status is low this will be excluded)
- Reported Medical History of Diabetes, Hypertension, Malignancies
- Time since diagnosis of osteoporosis
- Previous treatment for osteoporosis (before index date) or Number of different treatments for osteoporosis in the entire patient history available
- History of DVT or PE

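### The SAP 8.1.4 fallback counts event-free time before the index prescription as time at risk for comparators only, which would bias the bazedoxifene hazard ratio upward if the fallback is used

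*SAP*

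**What the plan says.** SAP 8.1.4 begins with newly prescribed women and measures time from the index prescription. It then adds a fallback. The trigger is "In the very unlikely event that the number of bisphosphonate or raloxifene patients are less than the number of BZA patients". The consequence is that "the analysis will be extended to include bisphosphonate and raloxifene patients whose treatment began prior to the enrolment period". For the women added, "For such patients the start date will be the first date of treatment for bisphosphonates or raloxifene, available within the database".

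Three other rules bear on this:

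- **Index date (SAP 5.4, and to the same effect 2.1):** the date of the "first recorded prescription for BZA or bisphosphonate or raloxifene during the study enrolment/accrual period".
- **Prior events (SAP 5.4):** a woman whose endpoint was "recorded prior to the index prescription will not be included in the analysis for that specific outcome". For VTE, such a woman "will be categorized as a prevalent case and will be excluded from the primary VTE analysis".
- **Time axis (SAP 8.1.4):** the Cox model is fitted on time from the beginning of treatment. Neither document mentions delayed entry or left truncation.

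SAP 2.1 starts follow-up for every endpoint at the index date, and SAP 8.1.2 starts person-years at the index prescription. The fallback departs from both.

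**The concern.** A woman added under the fallback must reach the enrolment period, receive a prescription in it, and have no recorded VTE before that prescription. She cannot contribute an analysed VTE between her first treatment in the database and her index date. The fallback nevertheless starts her clock at the earlier date. This is immortal time.

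The effect is one-sided. Enrolment opens at the BZA launch in each country, so BZA women have essentially no BZA treatment before it. Only the comparator hazard is diluted, and the BZA hazard ratio rises even if the drugs carry the same risk. In a post-authorisation safety study, that could create or enlarge an apparent VTE excess. SAP 8.2.4 calls the time-to-event analysis secondary, but SAP 4.2, 8.2.2 and 8.2.5 use the Cox hazard ratio and its test to compare treatments, including for the primary objective.

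**Working it through.** **1. Follow-up per woman (F).** The documents give no mean follow-up, so it was recovered from Protocol 7.1, Table 3. The Wald limits are IRR × exp(±1.96 × √(1/E1 + 1/E0)), with E = n × rate × F, the rate 1.74 per 1000 PY, and E1 multiplied by the IRR. Take F = 5 × 0.85 = 4.25 PY and the 1:6 row (1,750 and 10,500):

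- E0 = 10,500 × 0.00174 × 4.25 = 77.65. At IRR 1, E1 = 1,750 × 0.00174 × 4.25 = 12.94.
- IRR 1: √(1/12.94 + 1/77.65) = 0.300, giving 0.56 to 1.80 (table: 0.6, 1.8).
- IRR 1.5: E1 = 19.41, giving 0.91 to 2.47 (table: 0.9, 2.5).
- IRR 2: E1 = 25.88, giving 1.28 to 3.12 (table: 1.3, 3.1).

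F = 4.25 reproduces 22 of the 24 limits in Table 3. Exponential loss at 15% a year gives F = (1 − 0.85⁵)/(−ln 0.85) = 3.42, which reproduces 3 of 24. Five full years reproduces 12 of 24. F = 4.25 is used below.

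**2. Bias at a true ratio of 1.** Let f be the share of comparators with pre-index treatment and P their mean pre-index years. Neither is in the documents, so both are assumed. Let λ be the common rate.

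- Events per comparator: λF. Time counted: F + fP.
- Comparator rate: λF/(F + fP). BZA rate: λ.
- Apparent ratio: (F + fP)/F = 1 + fP/F.

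| f | P (years) | F = 4.25 | F = 3.42 | F = 5 |
|---|---|---|---|---|
| 0.25 | 1 | 1.06 | 1.07 | 1.05 |
| 0.5 | 2 | 1.24 | 1.29 | 1.20 |
| 0.8 | 2 | 1.38 | 1.47 | 1.32 |

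This is a person-time approximation to the Cox hazard ratio.

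**3. Check on the Cox model.** A simulation used a true hazard ratio of 1, 182,300 women per arm, 1.74 per 1000 PY, a 5-year maximum and 15% annual loss, with one run per scenario. Expected events per arm are 182,300 × 0.00174 × 3.42 ≈ 1,085, so each estimate carries noise of about 9% either way (1.96 × √(2/1,085) ≈ 0.084 on the log scale).

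- Clock from first treatment, no delayed entry, f from 0.25 to 1: hazard ratio 1.15 to 1.26 with a mean of 1 pre-index year, and 1.17 to 1.86 with 2.
- Stopping the clock 5 years after the start date: still 1.13 to 1.84 over the same scenarios.
- Delayed entry at the index date: 0.94 to 1.06 over all scenarios run, including a mean of 3 pre-index years. This is consistent with no bias.

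**4. Can the trigger fire?**

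- Bisphosphonate: 82,041 against 1,823 BZA (SAP 5.4). Not triggered.
- Raloxifene: SAP 2.1 reports about 68,000 treated women and says "Between 1 and 6% of these patients are taking raloxifene, depending on the region". That is 0.01 × 68,000 = 680 to 0.06 × 68,000 = 4,080. It falls below 1,823 if the share is under 1,823/68,000 = 2.7%.
- The comparison that matters is within the newly prescribed subgroup, and those counts are not given for any drug.
- The trigger refers to a shortage of either comparator, but the extension covers both. Read literally, a raloxifene shortfall would also bring earlier-treated women into the bisphosphonate group.

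**The case against.** The strongest reply is that this is a conditional sentence, described by the SAP itself as very unlikely to apply, inside an analysis that SAP 8.2.4 labels secondary. SAP 8.1.2 names cumulative incidence as the primary analysis. Its denominator is persons, and the person-time rates start at the index prescription, so neither is touched. All of that stands and limits the reach of the point.

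A reader might infer more than the documents support:

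- **That the primary VTE comparison is already biased.** On stated counts bisphosphonate does not trigger the rule. The primary comparison is reached only through a raloxifene shortfall and the both-comparators wording.
- **That the rule will probably fire for raloxifene.** Most of the 1 to 6% range lies above 2.7%. The newly prescribed restriction shrinks the BZA count too. The 68,000 is background text carried over from the protocol, and the current bisphosphonate group alone exceeds it. A shortfall is possible, not demonstrated.
- **That the ratio could nearly double.** With f = 0.8, P = 4 and F = 3.42 the formula gives 1.93. But 3.42 does not reproduce Table 3, and a mean of 4 prior years is close to all the Spanish history available when enrolment opened (data from 2006, enrolment from October 2010).
- **That the clock starts at the first prescription ever.** The SAP says the first one available in the database.

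The requirement for an osteoporosis code within 60 days before the index prescription may also keep f and P small. SAP 2.1 allows that criterion to be dropped, however, so it is not a secure limit. Finally, the sponsor may have intended VTEs after the earlier start date to count. The SAP does not say so, and entry would still require an enrolment-period prescription, so part of the problem would remain.

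**Conclusion.** The fallback is wrong as written. Its start date, the exclusion at the index prescription and the absence of delayed entry together add event-free risk time to comparators only, and the BZA hazard ratio moves upward. It also contradicts the index-date start in SAP 2.1, in 8.1.2 and at the opening of 8.1.4.

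The size is uncertain. With F = 4.25 PY, the approximate null ratio is 1.06 (f 0.25, P 1), 1.24 (f 0.5, P 2) or 1.38 (f 0.8, P 2). F is inferred from Table 3; f and P are assumptions. The bias would be smaller if the 60-day diagnosis criterion is kept and limits prior use. It arises only if the fallback is used, which the documents make possible for raloxifene but do not show to be likely. The point merits correction before the analysis because the cost is so low, not because the main result is known to be compromised.

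**What to change.** State in SAP 8.1.4 that, in the fallback, risk time starts at the enrolment-period index prescription. If time since first treatment is wanted as the time scale, specify delayed entry (left truncation) at the index date. In neither case should pre-index time count as time at risk. Reconcile the sentence with SAP 2.1 and 8.1.2, and say whether a shortfall in one comparator extends both.

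Do not add prior duration of the index drug as a covariate. It is structurally zero for BZA, so there is no overlap on which to adjust, and a covariate does not repair a misplaced time origin.

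The cost is one SAP sentence and an entry-time option in the Cox call. No new data are needed. The change removes the immortal time; it does not make prevalent and new users otherwise comparable, so the planned incident-user subgroup remains useful beside it.

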## **2.2. Endpoints**

The clinical endpoints for this study were determined based on the clinical and pre-clinical data from the bazedoxifene development program, class effects of other SERMs, and recommendations of the EU Rapporteurs.

Potential endpoints will be identified by an electronic search of the coded diagnosis fields of the medical records. The relevant diagnostic codes that will be used as operational definitions of each of the endpoints will be listed in the statistical analytic plan of the study. The available medical record of the identified cases for the primary endpoint will be retrieved and reviewed to confirm the diagnosis.

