### 7.1. Sample Size Calculation

There is no active de novo patient enrollment in this study and all women in the database who meet the inclusion criteria during the recruitment period will be included in the analysis. Therefore, the focus of the sample size calculation was to determine the precision of the estimated incidence rate ratios (IRR) that can potentially be achieved in the study depending on several different hypothetical scenarios of subject accrual. Depending on drug uptake in the participating countries, speed of accrual, event rates, and actual dropout rates, the precision of the estimated incidence rate ratio may change.

The estimates are based on the expected incidence rate of VTE as the primary endpoint. It is estimated that the incidence rate of VTE in women who are not treated with a SERM or HT is 1.74/1000 patient-years (PY), based on data from the placebo groups in bazedoxifene clinical trials. It is assumed that women treated with raloxifene would have a higher incidence of VTE, of 2.17/1000 PY, based on data from the Phase III pivotal trials of bazedoxifene. The rate of VTE observed in the raloxifene arm of the bazedoxifene pivotal trials is lower than the rate reported in the Multiple Outcomes of Raloxifene Evaluation (MORE) trial [1]. In the MORE trial, the incidence rate of VTE was 3.5/1000 patient-years in women randomized to raloxifene. Therefore, our calculations are likely to be substantially more conservative than estimates based on rates in the literature.

All estimates (Table 3, Table 4) were calculated with two-sided 95% confidence intervals. According to the study plan, there will be a 3-year accrual period and each woman will be followed for up to 5 years from enrollment. Since osteoporosis therapies are chronic therapies, it is likely that women will be exposed to the drugs for more than one year. A conservative annual loss to follow up rate of 15% was used in the estimation. Estimates were based on Wald 95% confidence intervals [2]

**Table 3: 95% Confidence Intervals (CI) for Incidence Rate Ratios (IRR) with different numbers of patients in the BZA arm and the primary comparator arm**

Bazedoxifene (n)	Bisphosphonate (n)	BZA:Bisphosphonate	Underlying Incidence Rate Ratio (IRR)		
			1	1.5	2
			95% CI of observed point estimate of IRR		
2150	8600	1:4	0.6, 1.7	1.0, 2.4	1.3, 3.0
2000	8000	1:4	0.6, 1.8	0.9, 2.4	1.3, 3.1
1750	10,500	1:6	0.6, 1.8	0.9, 2.5	1.3, 3.1
1500	12,000	1:8	0.5, 1.9	0.9, 2.5	1.3, 3.2

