2 INTRODUCTION

Note: in this document any text taken directly from the protocol is *italicised*.

Osteoporosis is characterised by a decrease in bone mass and architectural deterioration of bone tissue. Subtle modifications of bone remodelling, related to abnormalities of bone turnover, can induce a substantial loss of bone over a prolonged period of time. A period of asymptomatic bone loss results in reduced bone strength. When bone loss is sufficient to cause mechanical weakness, fractures may occur spontaneously or as a result of minimal trauma. Osteoporotic fractures cause a substantial clinical and economic burden for society. Age and menopause are the two main determinants of osteoporosis. The cessation of ovarian production of estrogen, at the time of the menopause, results in an accelerated rate of bone loss in women.

Bazedoxifene (BZA) is a third generation non-steroidal selective estrogen receptor modulator (SERM) currently approved in the European Union (EU) for the treatment of postmenopausal osteoporosis in women at increased risk of fracture. BZA is an estrogen receptor ligand that exhibits tissue specific activity: BZA functions as an agonist in the bone and an antagonist in the breast and uterine endometrium. BZA was developed in tablet form and current dosing consists of once daily administration of a 20 mg tablet. BZA (Conbriza) was approved in Europe via the centralized authorization procedure in April 2009. The first EU launch occurred in Spain in September 2010 which was followed by launch in Italy in April 2011.

Currently, one other SERM, raloxifene (Evista®) is marketed in Europe for the treatment and prevention of postmenopausal osteoporosis.

Bisphosphonates are non-hormone compounds that bind to the bone surface and are then taken up by osteoclasts. Bisphosphonates have a profound effect on bone remodeling, and are widely used for the prevention and treatment of osteoporosis.

In clinical trials, BZA-treated women had an increased risk of venous thromboembolic events (VTEs) compared to placebo. VTEs are included in the product label as an important identified risk.

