- Previous history of major lower extremity (hip, knee) arthroplasty, arthroscopic surgery (information on arthroscopic surgery not available in Italian database)
- General surgery, major orthopedic surgery (<1month prior to incidence of VTE)
- (Information on general surgery not available in Italian database)
- Multiple trauma (<1month prior to incidence of VTE)
- Hip, pelvis, or leg fracture (<1month prior to incidence of VTE)
- Stroke (<1month prior to incidence of VTE)
- Acute spinal cord injury (paralysis) (<1month prior to incidence of VTE)
- Hormone replacement therapy (limited information available in both databases)

A Cox model will be used in order to take into account the time varying component. The time from the beginning of the treatment (one among three types, BZA, raloxifene, and bisphosphonate) to the occurrence of primary end point is fitted in this model. The Proportional Hazards (PH) assumption will be tested for each covariable. If the PH assumption does not hold for some covariates, the use of time-varying HR for those covariates will be explored. If a categorical variable with more than 2 levels does not satisfy this PH assumption, collapsing some categories will be attempted to satisfy the PH assumption. Correlations between variables will also be evaluated in order to find independent factors and a final model that is clinically relevant.

First, the univariate analysis will be carried out on each covariable in order to determine the explanatory variables to be included in the final multivariate model. All significant variables with a p -value ≤ 0.20 in the univariate model will be taken into account in the multivariate Cox model.

If > 80% of the important risk factors for VTE listed above does not satisfy the PH assumption, a logistic regression analysis would be performed instead of Cox model to otherwise determine if the covariable is related to the incidence primary endpoint (VTE). The dependent variable would be the incidence of the primary end point during the follow-up period categorized as a binary variable. The 2 indicators of treatment group (BZA vs. bisphosphonates, raloxifene, will be forced in the multivariate model (Cox model or logistic model) to analyze incidence in each class of treatment, adjusted on

significant factors. Hazard ratios (HR) (odds ratios (OR) in case of logistic regression) with 95% Confidence intervals (CIs) and p-values will be presented.

[figure not shown]
Patients Switching Medications

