8.2 STATISTICAL ANALYSES

8.2.1 PATIENT CHARACTERISTICS

Descriptive statistics on available patient characteristics (e.g. age, BMI, smoking, history of relevant medical diagnoses) will be reported for all exposure groups at index date. A summary table will present and compare all the patients' demographic data at index date (BZA/raloxifene/bisphosphonates).

- Age (years): derived by difference between the year of time of interest and year of birth.
- Weight (kg): recorded at the given date, or if not available, at the most recent date before or it
- Height (cm): the value at the given date or, if not available, at the most recent date before or after it.

- Body Mass Index (BMI) (kg/m^2), calculated from weight and height as defined previously. BMI will be described in quantitative measure and in categorical data, as usual
- Alcohol use
- Smoking status
- Time since diagnosis of osteoporosis: derived by the difference between the index date and the diagnosis date.
- Previous treatment for osteoporosis (before index date) (yes versus no) or Number of different treatments for osteoporosis in the entire patient history available
- Previous history of VTE (Venous Thromboembolic Events) (before index date)
- Previous history of major lower extremity (hip, knee) arthroplasty, arthroscopic surgery (information on arthroscopic surgery not available in Italian database)
- General surgery, major orthopedic surgery (<1month prior to incidence of VTE) (information on general surgery not available in Italian database)
- Multiple trauma, (<1month prior to incidence of VTE)
- Hip, pelvis, or leg fracture (<1month prior to incidence of VTE)
- Stroke (<1month prior to incidence of VTE)
- Acute spinal cord injury (paralysis) (<1month prior to incidence of VTE)
- Hormone replacement therapy (limited information available in both databases)

If the diagnoses for any of the conditions listed in this section (8.2.1) are not found in the database, they will be assumed to be absent.

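### The prior-treatment covariate pools earlier raloxifene with earlier bisphosphonate use, and no planned analysis set is SERM-naive, so the effect of channelling from raloxifene to BZA on the VTE hazard ratio can be neither seen nor removed

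*SAP*

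**What the plan says.** SAP 8.1.4 lists, among the candidate covariates of the VTE model, "Previous treatment for osteoporosis (before index date) or Number of different treatments for osteoporosis in the entire patient history available". SAP 8.2.1 repeats the item and shows that its first option is a yes/no variable. Neither section names a drug or a class. The term is also not guaranteed a place in the model: "All significant variables with a p -value ≤ 0.20 in the univariate model" go forward, and only treatment group is forced in.

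The documents treat VTE as a class matter. The SAP introduction says "Currently, one other SERM, raloxifene (Evista®) is marketed in Europe". Protocol 2.2 says that the endpoints were chosen partly from "class effects of other SERMs". Protocol 7.1 adds: "It is assumed that women treated with raloxifene would have a higher incidence of VTE".

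Four other rules bear on the point:

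- **Prior VTE (SAP 5.4).** Women with a VTE before index leave the primary VTE analysis.
- **Index date (SAP 2.1).** Index is a woman's first prescription of any of the three study treatments within the enrolment period.
- **Populations (SAP 8.2.5).** Population (a) takes the full BZA group. Population (b) is the incident-user subgroup, in which a woman qualifies "if they have not had any treatment for osteoporosis in at least 6 months prior to the index date" (SAP 5.4).
- **Newly prescribed subgroup (SAP 8.1.4).** The time-to-event analysis starts with newly prescribed women whose osteoporosis was diagnosed during enrolment.

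**The concern.** A woman who took raloxifene and is still in the primary VTE analysis has been exposed to a SERM with no recorded VTE. A former bisphosphonate user has not been through that selection. On the plan's own premise the two histories carry different information about VTE risk on BZA, yet the covariate gives them one value.

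If former raloxifene users are over-represented among BZA women and their VTE rate on BZA is lower than that of SERM-naive women, the BZA rate falls for a reason unrelated to the drug's effect in new users. In a post-authorisation safety study whose primary question is VTE, a shift of that kind would make BZA look safer than it is. As the SAP stands, the report would not even show how many such women there are.

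**Working it through.** The documents give no figure for this point, so there is none to reproduce. The coding is checked first, then the possible size.

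**1. Coding.** Take two women with one earlier drug each.

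| Earlier drug | Yes/no | Count |
|---|---|---|
| Raloxifene only | yes | 1 |
| Bisphosphonate only | yes | 1 |

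Either version of the covariate gives them the same contribution in the model.

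**2. Subgroups.** Raloxifene stopped more than 6 months before index is compatible with incident-user status. Being newly prescribed and newly diagnosed does not exclude it either: Protocol 10 notes that raloxifene is also indicated for prevention.

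**3. Size.** Let f be the share of BZA person-time from women with earlier raloxifene, and h their VTE rate on BZA relative to SERM-naive women on BZA. If earlier raloxifene does not alter the rate in the bisphosphonate group, the hazard ratio is multiplied by

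(1 − f) + f·h = 1 − f(1 − h).

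Both f and h are assumptions. Anchors:

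- f: 1 to 6% of drug-treated women in the database take raloxifene (Protocol 3.1; SAP 2.1). This is not the share among BZA women, but it is the only related figure. The values 20% and 40% stand for channelling.
- h: removing the whole SERM excess on the planning rates in Protocol 7.1 gives 1.74/2.17 = 0.80. With the higher raloxifene rate quoted there, 1.74/3.5 = 0.50. The midpoint is 0.65.

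| f | h = 0.80 | h = 0.65 | h = 0.50 |
|---|---|---|---|
| 6% | 0.988 | 0.979 | 0.970 |
| 20% | 0.96 | 0.93 | 0.90 |
| 40% | 0.92 | 0.86 | 0.80 |

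A true ratio of 2.0 would be seen as 1.94 to 1.98 at 6%, 1.80 to 1.92 at 20% and 1.60 to 1.84 at 40%.

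If former raloxifene users are instead at higher risk, the sign reverses: f = 20% and h = 1.25 give 1 − 0.20 × (1 − 1.25) = 1.05.

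**4. Does the pooled term help?** Assume a true ratio of 2.0, h = 0.5, and earlier SERM use in 40% of previously treated BZA women. The ratio is 2.0 in untreated women and 2.0 × (1 − 0.4 × 0.5) = 1.6 in previously treated women.

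- Prior treatment in 50% of each arm: unadjusted 0.5 × 2.0 + 0.5 × 1.6 = 1.80. A Poisson model with the yes/no term also gives 1.80.
- Prior treatment in 80% of BZA and 50% of bisphosphonate women: unadjusted 0.2 × 2.0 + 0.8 × 1.6 = 1.68. With the yes/no term, 1.70.

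The term removes almost nothing.

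**5. Which analysis is exposed?**

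- *Cumulative risk (CR).* A woman with a raloxifene prescription during enrolment and BZA afterwards is indexed to raloxifene and stays there. Earlier raloxifene in the BZA cohort must therefore date from before enrolment opened (1 October 2010 in Spain, 1 May 2011 in Italy; SAP Table 1).
- *As-treated (AT).* The same woman contributes BZA time after switching, and a yes/no flag fixed at index misses raloxifene taken after index. A count over the whole record might include it but would not identify the drug. SAP 8.1.4 says that switchers' covariates at the event or end of follow-up would be considered, but not how prior treatment is updated.

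**The case against.** The case for leaving the plan alone has four parts.

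**The index rule already limits the problem.** This stands for CR. It does not stand for AT, which the SAP will report for all endpoints.

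**The direction is not established.** This stands. SAP 8.1.4 itself says that exposure changes often follow a drug's failure or its side effects, so women who leave raloxifene need not be low-risk survivors. A prior VTE may also go unrecorded, because hospital data are not collected systematically and only 6 months of history is required. A reader might infer that SERM-tolerant women do concentrate in the BZA cohort and hide harm, or that prior raloxifene and prior bisphosphonate point in opposite directions for VTE risk. The documents support neither: they show that the histories differ, not the sign of the net effect, and they link prior bisphosphonate use to VTE risk nowhere.

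**The size is small.** This stands near the 1 to 6% share. It fails only with channelling, which the documents neither show nor exclude.

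**A drug-specific flag alone would not solve it.** This largely stands. The mechanism concerns risk on BZA, so a main-effect term averaged over both arms cannot isolate it. Events would be few: 6% of 1,823 is about 109 women, and over 5 years at 1.74 to 3.48 per 1,000 patient-years (the planning rate and twice it) they yield 109 × 5 × 1.74/1000 = 0.9 to 109 × 5 × 3.48/1000 = 1.9 VTEs. Hence the need for a by-cohort table and a SERM-naive repeat.

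A reader might also infer that only comparator women can be continuing their index drug. That is not strictly so: both launches are dated to the month before enrolment opened. Continuing users are in any case kept out of the incident-user subgroup.

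**Conclusion.** The coding gap is real: earlier raloxifene is pooled with earlier bisphosphonate use, no planned analysis set is SERM-naive, and the pooled term would correct little if the selection exists. Bias in the BZA-bisphosphonate VTE hazard ratio is possible and plausibly toward the null, but its direction is not certain.

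At 6% the factor is about 0.98 to 0.99 for h of 0.65 to 0.80, which is small. It becomes material (for example 0.86 at 40% and h = 0.65) only if raloxifene users are channelled to BZA. These figures rest on assumed f and h and on no effect of earlier raloxifene in the bisphosphonate arm. Under CR, only raloxifene use before enrolment opened can matter; AT is more exposed.

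The conclusion concerns the primary comparison. Against raloxifene, the comparator cohort itself holds women with earlier SERM use, so a bias could cancel or reverse. The change is worth making because the present plan cannot tell the trivial case from the material one.

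**What to change.** 1. In SAP 8.2.1, derive prior raloxifene, prior bisphosphonate and other prior osteoporosis drug as separate variables from the prescription record, which holds the product prescribed, and tabulate them by cohort. For AT, derive them before the start of each exposure episode rather than before index only.
2. In SAP 8.1.4, use these in place of the pooled variable, and exempt prior raloxifene from the p ≤ 0.20 screen.
3. Add a sensitivity analysis that repeats the BZA-bisphosphonate VTE hazard ratio, CR and AT, in women with no recorded prior SERM.

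The cost is SAP wording and recoding of data already held. The downsides are a few more model terms with few events, and a SERM-naive status known only as far back as each woman's record goes. Data collection began in 2004 in Italy and 2006 in Spain, only 6 months of history is required, and SAP 7 treats an unrecorded treatment as absent. The report should state this limit.
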